Thursday June 3rd, 2021

TITLE: Enhancing Cognition in Older Persons: A Randomized Controlled Trial of Mindfulness-Based Stress Reduction (MBSR) and Transcranial Direct Current Stimulation (tDCS).

NCT03653351

METHODS

Study design and participants

We conducted a randomized, double blind, sham-controlled trial of tDCS combined with MBSR in adults aged 60 years or older with symptoms of depression or anxiety plus subjective cognitive complaints in two academic centers (Centre for Addiction and Mental Health, Toronto, ON, Canada; and Washington University in St. Louis, MO, USA). The study was approved by both institutional review boards and all participants provided written informed consent.

Participants were recruited between June 27, 2018 and March 6, 2019. They completed an initial phone screen followed by an in-person screening assessment, which included a review of medical history and medications to determine eligibility. Participants reported cognitive complaints but had intact cognitive function as ascertained by a Short Blessed Test [27] score ≤ 10 and a Montreal Cognitive Assessment (MoCA; [28]) score ≥ 25 . The Patient Reported Outcomes Measurement Information System (PROMIS) measures were used to assess depression and anxiety over the past seven days [29] including self-reported negative mood, views of self, social cognition, decreased positive affect, engagement self-reported fear, anxious misery, hyperarousal, and somatic symptoms related to arousal [30]. Participants were included if their baseline PROMIS 8-item depression score was ≥ 16 or their baseline PROMIS 7-item anxiety score was ≥ 14 , indicating moderate to severe symptoms.

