Prior to the initiation of the intervention, all participants completed tDCS training provided at the local academic hospital using a group format. During five one-hour group sessions provided over five consecutive days, participants were given an overview of the tDCS device and detailed instructions for administration, programming, resetting, electrode placement, and safety procedures (such as aborting sessions safely). They were also trained on how to troubleshoot tDCS problems, such as managing side effects e.g. tingling and itching, and self-record necessary data. At the end of training, participants were required to demonstrate their competency self-administering tDCS by passing an assessment administered by the study coordinators. Throughout the tDCS training sessions and the intervention trial, participants had access to a training video detailing the procedures to guide them through tDCS administration as needed. A manual and coordinator contact information was also provided to each participant, and the study coordinator was available to troubleshoot over the phone during at-home tDCS sessions.

The MBSR training was based on the program developed by Jon Kabat-Zinn at the Center for Mindfulness University of Massachusetts Medical School [14, 15]. The in-class MBSR training was conducted at the academic hospital using a group format over

approximately ten weeks; group sessions included an orientation session, 8 weekly 2.5-hour classes, and a half-day retreat. All participants were required to attend the MBSR in-person classes and instructed to refrain from discussing tDCS treatment amongst themselves to protect blinding. Content included instruction in mindfulness meditation, mindful movements, and discussion of home practices to enhance mindfulness in everyday life. At the end of each in-class session, the MBSR instructor gave the group a structured MBSR activity and associated audio files to complete at home for the week. The study used “A Mindfulness-Based Stress Reduction Workbook” as a companion guide [37]. In summary, participants attended weekly in-class group MBSR plus tDCS sessions at the hospital, and then asked to complete at least 30 minutes of guided MBSR and tDCS at home the other six days of the week.

Outcomes

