Trained research staff blinded to participants’ tDCS assignment performed pre- and post-intervention assessments. Follow-up assessments were performed within two weeks of completing the intervention. Feasibility was assessed by examining participants’ in-class attendance (i.e., number of in-person MBSR group sessions attended) and adherence to at-home mindfulness practice while using tDCS. Participants completed hand-written logs daily, detailing their at-home use of tDCS and the frequency and duration of MBSR practice; these self-report logs were used to determine the at-home adherence rates. To determine the at-home adherence rate, we first determined how many at-home sessions each participant completed by looking through the at-home logs. We then calculated the

total expected number of sessions that should have been completed at home over the period of the intervention. Lastly, we divided the total number of sessions each participant completed by the total number of expected sessions to get a percentage of at-home adherence. Participants also documented any failures of the tDCS device during stimulation and any adverse events (AEs). AEs that required the discontinuation of tDCS or MBSR were identified, as were serious adverse events (SAEs) defined as AEs that resulted in life-threatening health issues, hospitalization, or death.

The main cognitive measure was the Fluid Cognition Composite from the National Institutes of Health (NIH) Toolbox Cognition Battery [38], a computer-based instrument measuring both crystallized and fluid cognition. In addition, immediate memory and delayed recall were measured using a standard 16-word list validated at the Washington University Alzheimer's Disease Research Center that is sensitive to change and does not have ceiling effects in preliminary studies.

The Cognitive Affective Mindfulness Scale – Revised (CAMS-R; [39]) was used to measure the four domains of mindfulness – attention, present-focus, awareness, and acceptance. CAMS-R is a self-report measure of everyday mindfulness that is not specific to any one type of meditation. CAMS-R asks questions about translating and integrating the domains of mindfulness into everyday life, for example, being able to focus on the present moment, and keeping track of one's thoughts and feelings. CAMS-R

was administered pre- and post-intervention to determine how well participants integrated the teachings from MBSR into their everyday lives.

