In addition to the PROMIS measures of depression and anxiety, the two following PROMIS measures were used to assess satisfaction with, and ability to perform usual social roles and activities: the 8-item short form v2.9 PROMIS Scale for Satisfaction with Social Roles and Activities [40] and the 8-item short form v2.0 PROMIS Ability to Participate in Social Roles and Activities [40].

Statistical Analyses

All data were analyzed using the Statistical Program for Social Sciences (SPSS) version 25.0 [41]. Extreme outliers (± 3 standard deviations) were removed for each time point. Data were visually inspected for normal distribution and were checked statistically with the Shapiro-Wilk test. Chi-square and independent samples *t*-tests were used to evaluate differences between the active and sham tDCS groups on baseline demographic, clinical, and cognitive measures.

Measures of feasibility, tolerability, and safety were analyzed descriptively. While the primary goal of this pilot study was to assess feasibility, tolerability, and safety, preliminary evaluations of changes in efficacy measures were performed using repeated measures analyses of variance (RM-ANOVAs), with randomization as the between-subjects variable, and time-point (pre- or post-intervention) as the within-subjects

variable. For cognition, the three dependent variables were: NIH Toolbox Cognition Battery Fluid Cognition Composite, total recall score of the word list, and the delayed recall score of the word list. The effects of the intervention on subjective changes were explored with the following five dependent variables: CAMS-R, PROMIS depression scores, PROMIS anxiety scores, PROMIS satisfaction with social roles and activities, and PROMIS ability to participate in social roles and activities. For this pilot trial, a $p < 0.05$ was considered significant and no corrections were made for multiple comparisons.

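### Individual worsening on PROMIS depression and anxiety is not counted as a safety outcome; it reaches the safety results only through a self-recorded AE, a discontinuation or an SAE

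*Combined protocol and SAP*

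**What the plan says.** **Entry.** Under Study design and participants, entry requires a PROMIS 8-item depression score of at least 16 or a PROMIS 7-item anxiety score of at least 14, described as "indicating moderate to severe symptoms". The scales cover the previous seven days.

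**Exposure.** Under Interventions, the MBSR program runs for "approximately ten weeks; group sessions included an orientation session, 8 weekly 2.5-hour classes, and a half-day retreat". Participants combine MBSR with active or sham tDCS in the weekly class and at home on the other six days.

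**Assessments.** Under Outcomes: "Trained research staff blinded to participants’ tDCS assignment performed pre- and post-intervention assessments". Then: "Follow-up assessments were performed within two weeks of completing the intervention". No symptom scale is scheduled in between.

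**Analysis of the scales.** Under Statistical Analyses, "preliminary evaluations of changes in efficacy measures were performed using repeated measures analyses of variance (RM-ANOVAs"), with arm and time point as factors. On the symptom scales: "The effects of the intervention on subjective changes were explored with the following five dependent variables: CAMS-R, PROMIS depression scores, PROMIS anxiety scores", followed by the two social-role scales. Values beyond ±3 SD are removed at each time point.

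**Safety.** Under Outcomes, participants record adverse events of any kind. AEs that led to stopping tDCS or MBSR are identified, as are SAEs (life-threatening events, hospitalization or death). Under Statistical Analyses, feasibility, tolerability and safety are named as the primary goal and are analyzed descriptively. No safety measure uses a PROMIS score.

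**The concern.** The trial holds a before-and-after depression and anxiety score for each participant who completes both assessments. The population was enrolled because one or both of these scores were raised. The plan uses the scores only to ask whether the arm averages moved, which does not show how many people got worse.

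Three features make the average a weak safety check here.

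- Entry required a high score on at least one scale, so regression to the mean alone would tend to improve the average in both arms.
- The ±3 SD rule can remove a very high post-intervention score from the only analysis that uses the scale.
- The remaining route is self-recording. Someone already depressed or anxious at entry may not see worsening as an adverse event. The side effects that the documents name in connection with tDCS training are tingling and itching, and nothing prompts for mood or anxiety.

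At stake is whether the safety results can answer a simple question from scores already in hand: how many participants in each arm finished with more depression or anxiety than they started with?

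**Working it through.** The documents give no sample size, SD, correlation or expected change for PROMIS, so there is no stated figure to reproduce. The check has three parts.

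**1. Routes by which worsening can become visible**

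| Route | Covers | Misses |
|---|---|---|
| RM-ANOVA on PROMIS (efficacy) | Mean change by arm | Individual worsening; removed outliers; participants with no post score, since a pre/post change needs both values |
| Self-recorded AEs | Any event the participant writes down | Worsening not recognised or not recorded as an AE |
| AE discontinuations and SAEs | Worsening that stops treatment or is life-threatening, leads to hospitalization or is fatal | Worsening short of that |

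No route counts a rise in PROMIS as such.

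**2. Can a good mean coexist with individual worsening?** This is an illustration only; every input is assumed. Work in baseline SD units, with higher scores worse (as the entry cut-offs imply), equal pre and post variances and normal change. With mean improvement m and pre/post correlation r:

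- SD of change: s = √(2(1 − r))
- P(any rise) = 1 − Φ(m/s)
- P(rise of at least 0.5) = 1 − Φ((0.5 + m)/s)

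For m = 0.5:

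| r | s | Any rise | Rise of at least 0.5 baseline SD |
|---|---|---|---|
| 0.3 | √1.4 = 1.183 | 1 − Φ(0.423) = 34% | 1 − Φ(0.845) = 20% |
| 0.5 | √1.0 = 1.000 | 1 − Φ(0.500) = 31% | 1 − Φ(1.000) = 16% |
| 0.7 | √0.6 = 0.775 | 1 − Φ(0.645) = 26% | 1 − Φ(1.291) = 10% |

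For m = 0 and r = 0.5 (SD of change equal to baseline SD), 1 − Φ(0) = 50% rise at all and 1 − Φ(0.5) = 31% rise by at least 0.5 SD. So a sizeable count is expected even with no average effect, and an arm's count means little without the other arm beside it.

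**3. Can the outlier rule remove a worsened score?** The largest standardized deviation possible in a set of n values is (n − 1)/√n. At n = 10 this is 9/3.162 = 2.85; at n = 11 it is 10/3.317 = 3.02. The rule can therefore act once a set has at least 11 values. The documents do not say whether it is applied within arm or across arms, or how many values there are.

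**The case against.** A reader might infer that individual deterioration never reaches the safety results. The documents do not support that. Participants recorded adverse events of any kind, AE discontinuations and SAEs were identified, and nothing excludes psychiatric events. A participant who recorded worsening mood, stopped because of it or was hospitalized would appear.

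Nor do the documents support calling worsened mood the main expected harm, or saying that the report showed only averages. They are a methods text without results or a list of tables.

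The other objections, and what stands of each:

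- **The percentages are generic.** This stands. They come from normal-tail arithmetic on assumed inputs and would apply to any continuous outcome. They show that a favourable mean does not rule out individual worsening; they do not estimate this trial's rate.
- **A threshold count does not isolate harm.** This stands. Selection on PROMIS may also narrow the baseline SD, so that half an SD is a small change in raw points and more open to noise. It is a reason to show both arms and list the individual changes, not a reason to omit the table.
- **Those who worsen and withdraw may have no post score.** This stands. A table of observed scores alone would miss them, so missing scores must be counted alongside.
- **A mid-course measure is no longer possible.** This stands. The document is dated June 2021, is written in the past tense and gives recruitment as ending in March 2019.

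**Conclusion.** The point holds as a cheap improvement. PROMIS depression and anxiety are analyzed only as pre/post group means, after ±3 SD removal. Individual worsening on them is not defined or counted as a safety outcome, although safety belongs to the primary goal. The existing AE route is real but depends on the participant recording the event, or on worsening severe enough to cause discontinuation or an SAE.

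This conclusion rests on the text alone. Its size in this trial is unknown, because the illustrative ranges in the working depend on the assumed mean change, correlation, equal variances and normality, none of which the documents give. Nothing here shows that any participant was harmed.

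**What to change.** Add one table to the descriptive safety results, by arm, using all observed scores before any ±3 SD removal:

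1. The number and percentage of participants whose PROMIS depression score and, separately, anxiety score rose from baseline at all.
2. The same for a rise of at least a stated threshold, for example 0.5 baseline SD calculated over both arms together. Label this as a convention that the documents do not supply.
3. The number per arm with no post-intervention score, cross-referenced to AE discontinuations.
4. A listing of individual changes, so that a reader can apply another threshold.

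Read the active arm against sham, and add no hypothesis test. State as a limitation that no symptom score was taken between the pre- and post-intervention assessments, and that the post score covers seven days only. Worsening that arose during the program and eased before follow-up would not show on the scale.

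The cost is one table and one listing from data already collected. The downside is that some of the counted worsening will be measurement noise, which the text beside the table should say.
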